3.1.2.2 Safety Evaluation Phase of BMS-986158 Combination with Nivolumab

If combination therapy with nivolumab is pursued, the safety of the selected BMS-986158 dose when given in combination with nivolumab within the dose expansion phase will be evaluated by monitoring DLTs in the first 6 to 12 subjects treated across the different tumor cohorts receiving combination therapy. Once the selected dose of BMS-986158 in combination with nivolumab is deemed safe based on the DLT evaluation, the dose expansion will continue as planned in all cohorts.

The guidance for assessing the DLT-related safety and overall safety will be similar to that used in the monotherapy cohorts. The DLT safety monitoring during the dose evaluation phase including potential decision to de-escalate to a lower dose will be based on the mTPI-2 design⁴⁹ with target toxicity (DLT) rate of 29% (-2%, +4%), as presented in Table 3.1.2.2-1. The performance of the design is reported in Appendix 8.

Initially, the first 3 to 4 subjects treated in combination will be evaluated for DLT. If 0 or 1 DLT is observed during the DLT period established for BMS-986158, an additional 3 subjects will be treated at the same BMS-986158 dose level. A decision to stay at the same dose level by treating additional 3 to 4 subjects, to expand (continue enrollment) of all subjects treated with combination therapy across all tumor cohorts (declaring this dose to be safe), or to consider de-escalation will be guided by the number of subjects with DLTs observed during the dose evaluation phase and the posterior probability of DLT. (Table 3.1.2.2-1 and Table 3.1.2.2-2). Subjects who do not complete the DLT observation period for reasons other than DLTs will not contribute to this safety evaluation and can be replaced. De-escalation may be considered if the safety and tolerability

profile for the selected BMS-986158 dose is evaluated as not acceptable, after discussion between the investigator(s) and the Sponsor/Medical Monitor.

Evaluation					se by m						
			N	umber o	f DLT Ev	aluable P	articipan	ts Treate	d		
Ľ		3	4	5	6	7	8	9	10	11	12
a DLT	0	Е	Е	Е	Е	Е	Е	Е	Е	Е	Е
	1	Е	Е	Е	Е	Е	Е	Е	Е	Е	Е
nts v	2	D	D	D	S	Е	Е	Е	Е	Е	Е
cipaı	3	DU	D	D	D	D	D	S	S	Е	Е
parti	4	-	DU	DU	D	D	D	D	D	D	S*
r of]	5	-	-	DU	DU	DU	DU	D	D	D	D
Number of participants with	6	-	-	-	DU	DU	DU	DU	DU	D	D
Nu	7	-	-	-	-	DU	DU	DU	DU	DU	DU

Combination Safety Monitoring Guidance for DLT during Safety Table 3.1.2.2-1:

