MYC AMPLIFICAT	IONS			
Non-GC-DLBCL	5 to 9	5 to 9	5 to 9	15 to 27
OC w MYC amplifications		5 to 9	5 to 9	10 to 18
UCS		5 to 9	5 to 9	10 to 18

Table 3.1.2.4-1:Dose Expansion Planned Sample Size

Tumor Cohort and Group	Initial Monotherapy	Subsequent Monotherapy	Combination Therapy	Total
AR AMPLIFICATIO	NS			
CRPC	5 to 9	5 to 9	5 to 9	15 to 27
MUTATIONS				
RCC		5 to 9	5 to 9	10 to 18
NSCLC		5 to 9	5 to 9	10 to 18
UM		5 to 9	5 to 9	10 to 18
All Cohorts	25 to 45	70 to 126	70 to 126	165 to 297

Table 3.1.2.4-1:	Dose Expansion Planned Sample Size
------------------	---

The minimum overall planned sample sizes are based on Stage 1 initial enrollment, subsequent enrollment, and combination therapy enrollment subject counts per cohort. The maximums are determined similarly. The above assumes that the selected dose level administered in combination is deemed safe; alternately an additional 6 to12 subjects may need to be treated to assess safety at a lower dose level and to continue enrolling all combination therapy cohorts.

An additional 6 to 12 subjects may be enrolled to evaluate a lower dose of BMS-986158 in combination therapy as well as another 18 subjects may be enrolled to evaluate target gene engagement in tumors, and additional PK and safety characteristics in up to 2 cohorts at a different dose or schedule. Therefore, the potential total for expansion will be approximately up to 201 subjects if only monotherapy is pursued, and approximately up to 327 subjects if all planned expansion cohort subjects in monotherapy and combination therapy groups are pursued.

Administration of Additional Treatment Cycles:

Subjects may discontinue treatment due to disease progression, unacceptable AEs, or at the subject's request. Treatment decisions related to subject management will be based exclusively on RECIST version 1.1 (Appendix 4), the Lugano 2014 criteria (Appendix 9), or PCWG3 criteria (including PSA assessments) (Appendix 12). Subjects with an objective response of CR, partial response (PR) or stable disease, will continue therapy until they develop progressive disease (PD, unless in case of treatment beyond progression as detailed in Section 3.6), experience clinical deterioration, develop AEs requiring discontinuation of treatment or withdraw consent. Subjects who developed disease progression on BMS-986158 monotherapy in Part 2 will not be allowed to switch to combination therapy.

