- S: staying at the same dose if any subinterval within [27%, 33%] has the largest unit probability mass,
- D: de-escalating to the lower dose if any subinterval within (33%, 100%) has the largest unit probability mass.

At the end of the trial, MTD will be picked by isotonic regression estimation method to be the dose level whose estimated toxicity rate is closest to the target toxicity rate among all the evaluated dose levels.

Simulations were performed to examine the operating characteristics of mTPI-2 and 3+3 designs for this study. Escalation decisions based on the mTPI2 are shown in the protocol. Decisions based on the 3+3 design are shown below:

- E: no subject with DLT out of 3 DLT evaluable subjects initially, or at most 1 subject with DLT out of 6 DLT evaluable subjects after adding 3 more subjects.
- S: 1 subject with DLT out of 3 DLT evaluable subjects initially.
- D: at least 2 subjects with DLT out of 3 DLT evaluable subjects initially, or at least 2 subjects with DLT out of 6 DLT evaluable subjects after adding 3 more subjects at this dose

Settings for simulation:

- 6 dose-toxicity scenarios, each of which with a number of 2 (expected) dose levels
- 1000 trials per scenario
- Target toxicity (Pt) for mTPI-2 design: 29% with Equivalence Interval (EI) = [27, 33%]
- The mTPI-2: initial cohort size of 3 (or 4) followed by cohort size of 3 (or 4) for the remaining cohorts at the same (or lower if needed) dose level, requiring a minimum of 3 for a dose decision; Therefore cohorts of size 4 and a 25% dropout rate were used in the simulations.
- Stopping rule for mTPI-2: When there are already 12 DLT evaluable subjects treated at a dose level, and mTPI-2 suggested decision is to treat more subjects at this dose level, dose escalation can be stopped.
- Maximum number of DLT evaluable subjects for the study is 12.
- A nominal dose level of -1 is added in the tables to account for the case when de-escalation decision is made from dose level 1. However, the dose level -1 is not used in the simulations.
- A Beta(1,2) prior probability distribution is used which corresponds to a 33% expected DLT rate assumed for the combination of nivolumab with BMS-986158.

Dose-Toxicity Curve Scenarios

Six (6) scenarios of dose-toxicity (DLT) curves are selected to cover various possibilities and presented in the following figure with scenario ID shown at the end of line.

Scenario	DLT Rate at Dose Level 1	DLT Rate at Dose Level 2*
1	0.15	0.25
2	0.20	0.27

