3	0.15	0.30
4	0.25	0.35
5	0.30	0.35

Revised Protocol No.: 07 Date: 18-Mar-2019

6	0.35	0.45

*Starting dose level

Simulation Results

Simulation results are summarized from all the simulated trials per scenario, and include the following statistics:

- MTD Selected: Frequency of each dose level being selected as MTD.
- Subjects Allocated: Number of subjected being allocated to each dose level.
- DLT rate: The average number of subjects who have DLT across all dose levels.
- Average Sample Size: The average number of subjects across all dose levels.
- Early Stop Prob: mTPI-2 only. The frequency that mTPI-2 stopping rule was triggered during the trial.

Scenario 1		Dose Level		DLT	Average	Early Stop	
					Rate	Sample	Prob.
						Size	
True DLT Rat	e	-1	1 / 15%	2 / 25%			
MTD	3+3	20%	31%	49%			
Selected (%)	mTPI-2	9.5%	36%	54%			
	1111112	2.570	5070	5470			
Subjects	3+3		4.7	3.5		8.2	
Allocated (n)	mTPI-2		4.1	4.4		8.5	
Note: The mTPI-2 selects the MTD more frequently than does the 3+3, and the 3+3 selects no							
dose 10.5% more frequently than does the mTPI-2.							

Scenario 2		Dose Le	Dose Level		DLT Rate	Average Sample	Early Stop Prob.
			-	1		Size	
True DLT Rat	e	-1	1 / 20%	2 / 27%			
MTD	3+3	32%	28%	41%			
Selected (%)							
Selected (70)	mTPI-2	17%	43%	40%			
Subjects	3+3		4.8	3.0		7.8	
Allocated (n)	mTPI-2		4.2	3.9		8.1	
Note: The correct MTD is selected about as often by both designs but the 3+3 selects no dose							
as the MTD 15% more frequently than does the mTPI-2.							

Scenario 3		Dose Level		DLT Rate	Average Sample Size	Early Stop Prob.	
True DLT Rate		-1	1 / 15%	2 / 30%			
MTD Selected	3+3	22%	36%	42%			
(%)	mTPI-2	11%	46%	43%			
Subjects	3+3		4.9	3.5		8.3	
Allocated (n)	mTPI-2		4.2	4.3		8.5	
Note: The correct MTD is selected as often by both designs, but the 3+3 selects no dose (-1)							

Note: The correct MTD is selected as often by both designs, but the 3+3 selects no dose (-1) twice as frequently (22% vs. 11%) than does the mTPI-2.

Scenario 4	4		Dose Level		DLT Rate	Average Sample Size	Early Stop Prob.
True DLT Rate		-1	1 / 25%	2/35%			
MTD Selected	3+3	42%	33%	25%			
(%)	mTPI-2	24%	51%	25%			
Subjects	3+3		5.0	2.7		7.7	
Allocated (n)	mTPI-2		4.4	3.5		7.9	
Notes: The higher dose is selected 25% of the times by both designs, the mTPI-2 selects the correct MTD 18% more often than does the 3+3. The 3+3 selects no dose more frequently (18% more) than does the mTPI-2.							

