Scenario 5		Dose Level		DLT Rate	Average Sample Size	Early Stop Prob.	
True DLT Rate		-1	1 / 30%	2/35%			
MTD Selected	3+3	54%	25%	21%			
(%)	mTPI-2	30%	49%	22%			
Subjects	3+3		5.0	2.2		7.2	
Allocated (n)	mTPI-2		4.3	3.4		7.7	
Notes: The mTPI-2 design selects the correct dose as the MTD almost twice as often as the 3+3							
(24% more frequently) and the 3+3 selects no dose 24% more frequently than does the mTPI-2.							

Scenario 6		Dose Level		DLT Rate	Average Sample Size	Early Stop Prob.	
True DLT Rate		-1	1 / 35%	2/45%			
MTD Selected	3+3	69%	22%	8.2%			
(%)	mTPI-2	44%	46%	11%			
Subjects	3+3		4.9	1.6		6.5	
Allocated (n)	mTPI-2		4.4	2.6		7.0	
Notes: The mTPI-2 design selects the dose with 35% toxicity more than twice as often as the							
3+3 (24% more frequently) and selects the top toxic dose 3% more often than the 3+3. The 3+3 selects no dose 25% more frequently than does the mTPI-2.							

Table 1:

LUGANO 2014 CLASSIFICATION FOR INITIAL EVALUATION, **APPENDIX 9** STAGING, AND RESPONSE FOR HODGKIN LYMPHOMA

Revised Criteria for Response Assessment

Response and Site	PET-CT-Based Response	CT-Based Response
Complete	Complete metabolic response	Complete radiologic response (all of the following)
Lymph nodes and extralymphatic sites	Score 1, 2, or 3" with or without a residual mass on 5PS1 It is recognized that in Waldeyer's ring or extranodal sites with high physiologic uptake or with activation within spleen or marrow (eg, with chemotherapy or myeloid colony-stimulating factors), uptake may be greater than normal mediastinum and/or liver. In this circumstance, complete metabolic response may be inferred if uptake at sites of initial involvement is no greater than surrounding normal tissue even if the tissue has high physiologic uptake	Target nodes/nodal masses must regress to ≤ 1.5 cm in LDi No extralymphatic sites of disease
Nonmeasured lesion	Not applicable	Absent
Organ enlargement	Not applicable	Regress to normal
New lesions	None	None
Bone marrow	No evidence of FDG-avid disease in marrow	Normal by morphology, if indeterminate, IHC negative
artial	Partial metabolic response	Partial remission (all of the following)
Lymph nodes and extralymphatic sites	Score 4 or 51 with reduced uptake compared with baseline and residual massles) of any size	 50% decrease in SPD of up to 6 target measurable nodes and extranodal sites

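### Appendix 8's printed results cannot come from a run that starts at the selected dose, as its own label and Section 3.1.2.2 require, so the stated performance of the combination safety rule must be rerun

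*Protocol*

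**What the plan says.** Section 3.1.2.2 evaluates the combination at the selected BMS-986158 dose. Three to four subjects are assessed first, and three more are added if there are 0 or 1 DLTs. Table 3.1.2.2-1 (mTPI-2, target 29%, interval 27% to 33%) and the posterior probabilities in Table 3.1.2.2-2 then guide whether to expand, stay or de-escalate, over 6 to 12 subjects. The section closes by naming 0 of 6, 1 of 9 or 2 of 12 DLTs as results that may be considered safe enough to open enrollment. On operating characteristics it says: "The performance of the design is reported in Appendix 8". Section 3.1.2.4 adds: "An additional 6 to 12 subjects may be enrolled to evaluate a lower dose of BMS-986158 in combination therapy".

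Appendix 8 simulates two dose levels in six scenarios, 1000 trials each. A footnote marks dose level 2 as "Starting dose level", and later mTPI-2 cohorts are described as "for the remaining cohorts at the same (or lower if needed) dose level". At least 3 evaluable subjects are needed for a decision. On cohort size it states: "Therefore cohorts of size 4 and a 25% dropout rate were used in the simulations". Its stopping rule works per dose ("When there are already 12 DLT evaluable subjects treated at a dose level"), but it also sets a limit for the whole study: "Maximum number of DLT evaluable subjects for the study is 12". The scenario 6 note says that mTPI-2 "selects the top toxic dose 3% more often than the 3+3".

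**The concern.** A trial that begins at dose level 2 must put its first cohort there, so the average number treated at dose level 2 cannot fall below 3. Several printed averages do. If the simulation ran upward from dose level 1, dose level 2 could be selected only in trials that first passed dose level 1. The printed chance of settling on dose level 2 would then belong to a different trial from the one in Section 3.1.2.2.

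In scenarios 4 to 6 the true DLT rate at dose level 2 is 35%, 35% and 45%, all above the 33% upper limit of the interval. The figure at stake is therefore the stated chance of declaring an over-toxic combination dose acceptable. Section 1.1.6 relies on Appendix 8 to prefer mTPI-2 to the 3+3, Section 7 provides no data monitoring committee, and Table 3.1.2.4-1 plans up to 126 combination subjects beyond this check.

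**Working it through.** **1. Allocation check (no modelling).** A start at dose level 2 gives an average of at least 3 subjects there. For mTPI-2, cohorts of 4 with 25% dropout average 4 × 0.75 = 3 evaluable. Printed averages at dose level 2 are 2.7, 2.2 and 1.6 (3+3, scenarios 4, 5, 6) and 2.6 (mTPI-2, scenario 6). These are not misprints of a total, because the allocations sum to the printed sample sizes: 5.0 + 2.7 = 7.7, 5.0 + 2.2 = 7.2, 4.9 + 1.6 = 6.5, 4.4 + 2.6 = 7.0.

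**2. Reproducing the 3+3 rows.** From Appendix 8's rule, for a true DLT rate p let a = (1−p)³ (0 of 3), o = 3p(1−p)² (1 of 3), and q = a + o·a (dose passes).

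- Upward from dose 1, adding three subjects at dose 1 to make six if dose 2 fails: P(dose 2) = q₁q₂; P(dose 1) = (1−q₂)[o₁a₁ + a₁(a₁+o₁)]; mean subjects at dose 2 = q₁(3+3o₂).
- From dose 2 downward: P(dose 2) = q₂; P(dose 1) = (1−q₂)q₁; P(none) = (1−q₂)(1−q₁); mean subjects at dose 2 = 3+3o₂.

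Scenario 1 (15%, 25%): a₁ = 0.6141, o₁ = 0.3251, q₁ = 0.8138; o₂ = 0.4219, q₂ = 0.5999. Upward, P(dose 2) = 0.8138 × 0.5999 = 48.8%, P(dose 1) = 0.4001 × (0.1997 + 0.5768) = 31.1% and P(none) = 20.1%, with 0.8138 × 4.266 = 3.47 subjects at dose 2. Downward, P(none) = 0.4001 × 0.1862 = 7.5%, with 4.27 subjects at dose 2.

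| Scenario | Printed 3+3 (none/dose 1/dose 2) | Exact, upward | Exact, from dose 2 | Subjects at dose 2: printed / upward / from dose 2 |
|---|---|---|---|---|
| 1 | 20/31/49 | 20.1/31.1/48.8 | 7.5/32.6/60.0 | 3.5 / 3.47 / 4.27 |
| 2 | 32/28/41 | 31.5/29.0/39.5 | 12.9/31.4/55.7 | 3.0 / 3.04 / 4.29 |
| 3 | 22/36/42 | 20.5/39.3/40.2 | 9.4/41.2/49.4 | 3.5 / 3.52 / 4.32 |
| 4 | 42/33/25 | 44.0/32.2/23.8 | 24.2/36.2/39.6 | 2.7 / 2.60 / 4.33 |
| 5 | 54/25/21 | 55.0/25.4/19.6 | 30.5/29.8/39.6 | 2.2 / 2.14 / 4.33 |
| 6 | 69/22/8.2 | 66.3/24.4/9.3 | 46.2/30.4/23.4 | 1.6 / 1.68 / 4.23 |

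The upward run agrees within about 3 points and 0.1 subject throughout. The labelled start misses by more than 7 points on dose 2 in every scenario; the Monte Carlo standard error with 1000 trials is at most 1.6 points. Swapped column headings do not explain it: from dose 2, scenario 1 puts 0.4001 × 3.975 = 1.6 subjects at dose 1, and the printed columns are 4.7 and 3.5.

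**3. mTPI-2 allocations.** Table 3.1.2.2-1 is reproduced in every cell from the Beta(1,2) prior and the 27% to 33% interval. Simulating it upward with three cohorts of 4 and 25% dropout gives 4.14/4.4 subjects in scenario 1 (printed 4.1/4.4) and 4.4/2.7 in scenario 6 (printed 4.4/2.6).

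**4. mTPI-2 as Section 3.1.2.2 plans it.** Start at the selected dose in cohorts of 3, with E from six subjects meaning expand. At p = 35%, one cohort has 0 DLTs with probability 0.2746, 1 with 0.4436 and 2 with 0.2389.

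- At 6, with 0 or 1 DLT (E): 0.2746² + 2 × 0.2746 × 0.4436 = 0.319. With 2 DLTs (S): 0.2746 × 0.2389 + 0.4436² = 0.262.
- At 9, with 2 DLTs (E): 0.262 × 0.2746 = 0.072. With 3 DLTs (S): 0.262 × 0.4436 = 0.116.
- At 12, with 3 DLTs (E): 0.116 × 0.2746 = 0.032.
- Sum: 0.319 + 0.072 + 0.032 = 42.3%. The same steps at p = 45% give 21.6%.

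Other readings of the expansion trigger:

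| Expansion opens when | True rate 35% | True rate 45% |
|---|---|---|
| E at 6 or more | 42% | 22% |
| E at 9 or more | 37% | 16% |
| E at 12 | 31% | 12% |
| 0/6, 1/9 or 2/12 guide | about 20% | about 7% |
| Printed in Appendix 8 | 25% and 22% (scenarios 4, 5) | 11% (scenario 6) |

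Varying the cohort pattern (3 or 4) moves the first row to 37–45% and 19–26%.

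**5. Cap.** Up to 12 at the selected dose plus up to 12 at a lower dose is 24, not 12.

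**The case against.** The strongest reply concerns mTPI-2, the design actually used. A reader might infer that Appendix 8 states half the true risk of expanding at an over-toxic dose: 25/42.3 = 0.59, 22/42.3 = 0.52, 11/21.6 = 0.51. That holds only if E from six subjects opens expansion on the table alone. Section 3.1.2.2 also brings in posterior probabilities and discussion, and under its 0/6, 1/9, 2/12 guide the printed figures are slightly too high. The printed quantity is also an end-of-trial isotonic selection, not a probability of expanding, and Appendix 8 gives no tie-break. In upward simulations, dose 2 is selected in 24%, 19% and 12% of trials in scenarios 4 to 6 with ties to the lower dose, and in up to 43%, 36% and 22% with ties to the higher. This objection stands, and the mTPI-2 size must be given as a range.

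A reader might also blame the cap of 12. The documents do not support that as the cause: from dose 2, raising the simulated cap from 12 to 24 moves selection of dose 2 only from 43/42/22% to 44/43/20%. Nor is the chance of selecting no dose shown to be generally overstated for mTPI-2. In scenario 6 the table-only rule gives (1 − 0.216) × (1 − 0.423) = 45%, against 44% printed.

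Finally, combination therapy is conditional, lies outside the SAP's scope, and remains under the interruption rule in Section 3.1.2.4 once expansion opens. This limits the consequence but does not make the tables right. If the footnote is the error and the upward run was intended, the simulation still does not describe Section 3.1.2.2.

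**Conclusion.** Appendix 8 is wrong as written. The allocation contradiction needs no assumption, and the upward start is a firm inference from the 3+3 match in all six scenarios. For the 3+3, a start at dose level 2 gives 39.6/39.6/23.4% selection of an over-toxic dose 2 in scenarios 4 to 6 (printed 25/21/8.2%), and 7.5% no dose in scenario 1 (printed 20%). For mTPI-2 the figure for the planned rule lies between about 20% and 42% at a true rate of 35%, and between about 7% and 22% at 45%, in cohorts of 3, depending on the expansion trigger. The printed values are about half only under the table-only reading. The study-wide cap is a separate inconsistency. Nothing here shows that Table 3.1.2.2-1 is miscalculated.

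**What to change.** Reconcile the starting-dose footnote, the simulation and Section 3.1.2.2. Rerun Appendix 8 for both designs from the selected dose, with the cap applied per dose level. State the expansion trigger, the MTD selection rule and the tie-break used, and whether caps count enrolled or evaluable subjects. Show results under both the table rule and the 0/6, 1/9, 2/12 guide, and replace the tables and scenario notes. The decision table and the doses do not change. The cost is a simulation rerun and new appendix pages, and some stated risks become less favourable.

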APPENDIX 10 MANAGEMENT ALGORITHMS FOR IMMUNO-ONCOLOGY AGENTS

These general guidelines constitute guidance to the Investigator and may be supplemented by discussions with the Medical Monitor representing the Sponsor. The guidance applies to all immuno-oncology agents and regimens.

A general principle is that differential diagnoses should be diligently evaluated according to standard medical practice. Non-inflammatory etiologies should be considered and appropriately treated.

Corticosteroids are a primary therapy for immuno-oncology drug-related adverse events. The oral equivalent of the recommended intravenous (IV) doses may be considered for ambulatory patients with low-grade toxicity. The lower bioavailability of oral corticosteroids should be taken into account when switching to the equivalent dose of oral corticosteroids.

[figure not shown]
Consultation with a medical or surgical specialist, especially prior to an invasive diagnostic or therapeutic procedure, is recommended.

The frequency and severity of the related adverse events covered by these algorithms will depend on the immuno-oncology agent or regimen being used.

GI Adverse Event Management Algorithm

Rule out non-inflammatory causes. If non-inflammatory cause is identified, treat accordingly and continue I-O therapy. Opiates/narcotics may mask symptoms of perforation. Infliximab should not be used in cases of perforation or sepsis.

[figure not shown]

Revised Protocol No.: 07 Date: 18-Mar-2019

corticosteroids.

Renal Adverse Event Management Algorithm

[figure not shown]
Rule out non-inflammatory causes. If non-inflammatory cause, treat accordingly and continue I-O therapy

Patients on IV steroids may be switched to an equivalent dose of oral corticosteroids (e.g. prednisone) at start of tapering or earlier, once sustained clinical improvement is observed. Lower bioavallability of oral corticosteroids should be taken into account when switching to the equivalent dose of oral corticosteroids.

Pulmonary Adverse Event Management Algorithm

[figure not shown]
Rule out non-inflammatory causes. If non-inflammatory cause, treat accordingly and continue I-O therapy. Evaluate with imaging

improvement is observed. Lower bioavailability of onal conticosterioids should be taken into account when switching to the equivalent dose of onal contros terolds.

Hepatic Adverse Event Management Algorithm

[figure not shown]
Rule out non-inflammatory causes. If non-inflammatory cause, treat accordingly and continue I-O therapy. Consider imaging for obstruction.

Refer to http://livertox.nih.gov/ for a compendium of agents that may cause liver injury

Endocrinopathy Management Algorithm

Rule out non-inflammatory causes. If non-inflammatory cause, treat accordingly and continue I-O therapy. Consider visual field testing,

[figure not shown]

Revised Protocol No.: 07 Date: 18-Mar-2019

switching to the equivalent dose of oral corticosteroids.

Skin Adverse Event Management Algorithm

Rule out non-inflammatory causes. If non-inflammatory cause, treat accordingly and continue I-O therapy.

[figure not shown]

Improvement is observed. Lower bioavailability of oral conticosteroids should be taken into account when switching to the equivalent dose of oral conticosteroids.

•Refer to NCI CTCAE will for term-specific grading criteria. •If SIS/TEN is suspected, withhold I-O the rapy and refer patient for specialized care for assessment and treatment. If SIS or TEN is diagnosed, permanently discontinue HO therapy.

Neurological Adverse Event Management Algorithm

Rule out non-inflammatory causes. If non-inflammatory cause, treat accordingly and continue I-O therapy.

Patients on IV steroids may be switched to an equivalent dose of oral corticosteroids (e.g. prednisone) at start of tapering or earlier, once sustained clinical improvement is observed. Lower bioavailability of oral corticosteroids should be taken into account when switching to the equivalent dose of oral corticosteroids.

